5. RANDOMISED CONTROLLED STUDY

Aim: To evaluate the effect of a soluble fibre supplement in glucose metabolism in pregnant women at high risk of developing gestational diabetes.

Study methodology: 12 week randomised, placebo-controlled, single-blinded study.

Intervention: Women will first be categorised according to their glycaemic status into two groups: GDM and glucose tolerant women. Afterwards, each group will be randomised into two groups and given either

- 1) Fibre supplement (Guar gum)
- 2) Placebo (Cellulose)

The participants will take the dietary supplement three times a day for 12 weeks. They will receive regular antenatal control according to NICE guidelines recommendations. Compliance will be addressed by weekly phone calls.

Number of volunteers: The number of participants will be arbitrarily define as no data of this type of intervention exists in this cohort. 40 participants will be recruited. Previous studies, outside pregnancy, have observed metabolic effects in samples of 15-40 subjects.

Recruitment: Women will be recruited in the antenatal clinic at Queen Charlotte and Chelsea's Hospital. An information sheet will be provided to eligible women in the first antenatal visit to explain the purposes of the study. Women who decide to take part will be asked to sign a consent form.

Randomisation: Initially women will be categorised according to glycaemic status in two cohorts: **Glucose tolerant** and **Early gestational diabetes (GDM)** cohort. Each of the two cohorts will then be independently randomised to either intervention or standard care using the sealed envelope website. Guar gum (intervention) and cellulose (placebo) will be provided in identical packed sachets.

STUDY OUTCOME MEASURES

PRIMARY OUTCOME MEASURES

- Glucose values at 0 and 120 minutes during an OGTT performed at 28 weeks in the glucose tolerant group.
- Glycaemic control assessed by need of insulin treatment (yes/no), days to insulin treatment and total insulin dose.

SECONDARY OUTCOME MEASURES

Assessing insulin sensitivity and insulin secretion at 28 weeks of pregnancy in the glucose tolerant cohort of women through validated indices using glucose and insulin (or C-peptide) values derived from the OGTT.

- Insulin sensitivity will be assessed using the Matsuda formula (18).
- Insulin secretion will be assessed by second-void fasting UCPCR as described by McDonald et al (19).

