6. ASSESSMENT AND FOLLOW UP

Women will be assessed by the researchers at four different visits. At the first antenatal visit, the general care team will mention the study, if the patient consents, she will then be approached by the researchers to explain the study protocol. At the second visit, when the OGTT is performed, women who decided to take part in the study will sign the consent form. At the next antenatal visit where results from the OGTT are explained, women included will be randomised. The last research visit will take place at 28 weeks gestation. Additionally, they will be contacted weekly, by telephone to assess compliance and confirm willingness to participate in the study. All participating women will continue to attend routine follow up by the Obstetrics team at the antenatal clinic. Women diagnosed with GDM in early pregnancy will continue their routine care under the Obstetric team at Queen Charlotte's Hospital. We will be collecting information regarding treatment from the notes taken at this follow-up visits.

1st visit (≤16 weeks gestation)

Women with a previous history of GDM will be considered at high risk of recurrence and will be referred to the antenatal clinic before 16 weeks of pregnancy. At this first visit, the direct care team will inform them about the study and ask them if they are willing to speak with a member of the research team. If they agree, a research team member will explain the protocol and invite them to participate in the study. An information sheet will be provided and women will have time to consider if they are willing to participate and inform the research team at their next antenatal visit.

2nd visit

Women who decide to participate will inform the research team when they attend their second antenatal visit, when an OGTT is to be performed. In this visit, women willing to participate will be asked to sign a consent form.

As part of the standard pregnancy care, these women will be booked for GDM early screening. The following investigations will be performed as part of their usual NHS care:

- Blood tests: full blood count, renal function. GAD antibodies can be requested in women in whom type 1 diabetes is suspected.
- Urine sample to test for proteinuria, glycosuria, leucocytes and nitrates.

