- Women from the **Glucose tolerant cohort** will undergo a second OGTT. Blood and urine samples will be collected at 0 and 120 minutes. Glycaemic status will then be assessed with the endpoint being the diagnosis of GDM (yes/no). Insulin sensitivity and insulin secretion will be estimated using the same parameters as in the first visit. As part of the study, women will be weight to calculate BMI and gestational weight gain at 28 weeks gestation. The research team will have their last face to face visit with the participant to discontinue the intervention and answer any potential questions about the study.
- In women in the **Early GDM cohort**, glycaemic control will be assessed by the need of insulin treatment (yes/no) and in those requiring insulin the days-to-treatment (insulin) and total insulin dose will be recorded. Data will be obtained by reviewing medical records. As part of the study, women will be weight to calculate BMI and gestational weight gain at 28 weeks gestation. The research team will have their last face to face visit with the participant to discontinue the intervention and answer any potential questions about the study.

PROCEDURES

Women will be advised to fast for 10 hours the night before the oral glucose tolerance test. They will also be advised not to restrict carbohydrate ingestion the three days prior to the OGTT. At the antenatal clinic, blood samples will be collected at baseline (0 min) and at 120 min after the administration of an oral load of 75 g of glucose.

In the baseline sample other parameters will also be determined. Creatinine and HbA1c will measure in all participants and GAD antibodies will be requested in women in whom type 1 diabetes is suspected.

Serum insulin and C-peptide will be collected at 0 and 120 min during the OGTT.

Women will be advised to void their first urine before attending the antenatal clinic. Second-void fasting urine sample will be collected at 0 min during the OGTT. A second urine sample will be collected at 120 min. Urinary C-peptide will measure in these samples will be transfer to boric acid containers, the aliquoted into 1 ml cryotubes and stored at -80 °C until analysis. Serum creatinine will be collected at baseline (0 min) and measure in the central lab. The urinary C-peptide creatinine ratio (UCPCR) will be calculated using these data.

ASSESSMENTS

(i) Gestational diabetes

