Gestational diabetes will be diagnosed if fasting plasma glucose >5.6 mmol/L and/or 120 min plasma glucose >7.8 mmol/L after the glucose load administered in the OGTT. Women with fasting plasma glucose <5.6 mmol/L and 120 min plasma glucose <7.8 mmol/L will be classified as “Glucose tolerant”.

(ii) Insulin sensitivity

Insulin sensitivity will be assessed using the Matsuda index as originally described (18) (Equation 1) and using two modified Matsuda equations in which insulin is substitute by either serum or urinary C-peptide (21,22) (Equations 2 and 3).

Equation 1.

$$\text{ISOGTT} = 10,000 / \sqrt{[\text{FPG} \times \text{fasting insulin}] \times [\text{mean glucose} \times \text{mean insulin during OGTT}]}$$

Equation 2.

$$\text{ISOGTT-} \text{C-pep} = 500,000 / \sqrt{[\text{FPG} \times \text{FsC-pep}] \times [\text{mean glucose} \times \text{mean sC-pep during the OGTT}]}$$

Equation 3.

$$\text{ISOGTT-UCPCR} = 500,000 / \sqrt{[\text{FPG} \times \text{UCPCR}_{\text{pmol}/\text{mmol}}] \times [\text{mean glucose} \times \text{mean UCPCR during the OGTT}]}$$

* FPG= fasting plasma glucose. FsC= fasting serum C-peptide. FUCPCR= fasting urinary C-peptide creatinine ratio.

(iii) Insulin secretion

[figure not shown]
Insulin secretion will be estimated by the UCPCR obtained using the fasting second-void urine sample, as it is strongly correlated with serum insulin, serum C-peptide (19) and 24-h urinary C-peptide (20).

Insulin response will be estimated using the UCPCR calculated with 120 min post-OGTT urine sample, as it is strongly correlated with the C-peptide and insulin area under the curve (19).

(iv) Need of insulin treatment, Days to insulin treatment and Total insulin dose

Medical records of women in the Early GDM cohort will be reviewed in order to determine the need of insulin treatment (yes/no) at 28 weeks gestation. In women requiring insulin treatment at any time during follow up, days-to-insulin treatment, calculated from randomisation day to the day insulin treatment is prescribed, and total insulin dose, calculated as the total dose of insulin international units (IU) divided by weight in Kg (insulin UI/Kg), will be recorded

Timeline for randomised controlled study

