7. PARTICIPANT ENTRY

PRE-RANDOMISATION EVALUATIONS

Women will be evaluated by the mid-wife at the first visit in the antenatal clinic. An OGTT will be booked to test for early GDM in women with previous GDM considered at high risk of recurrence. Personal and medical history will be recorded. When women attend for the OGTT, blood and urine samples will be collected at 0 and 120 minutes.

INCLUSION CRITERIA

- Women with a history of GDM in previous pregnancies
- Age \geq 18 years
- Singleton pregnancy
- \leq 16 weeks gestation

EXCLUSION CRITERIA

- Women unable or unwilling to give consent
- Pre-gestational diabetes or use of anti-diabetic medication in the first visit
- Significant chronic medical conditions (cardiovascular, liver or kidney disease)
- Women participating in other medical trial
- Women who have undergone bariatric surgery
- Women with milk allergy/intolerance
- Women unable to speak/understand English

WITHDRAWAL CRITERIA

Participants will be free to withdraw at any time and are not required to give a reason.

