9. STATISTICS AND DATA ANALYSIS

Data handling and analysis will be carried out by SPSS version 20.0 version.

No power calculation to decide sample size will be used. The number of participants has been arbitrarily defined, as it is a pilot study. We aim to recruit 40 women.

Before randomisation, women will be categorised according to their glycaemic status in two cohorts: Glucose tolerant and GDM. Each of these two cohorts will be randomly allocated into the

intervention (soluble fibre supplement) and control (placebo) group. Randomisation will be by sealed envelopes. Participants but not researchers will be blinded as to the type of intervention prescribed.

Differences between group in each cohort will be assessed using Student t test or Mann-Whitney U test for numeric variables depending on distribution; χ^2 will be used for categorical variables.

In the Glucose tolerant women cohort:

For the primary outcome, GDM (yes/no), logistic regression analysis will be performed.

For the secondary outcomes, insulin sensitivity and insulin secretion, linear regression analysis will be performed.

In the early GDM cohort:

For the primary outcome, need for insulin treatment (yes/no), logistic regression analysis will be performed. Additionally days-to-treatment analysis will be performed for those participants starting insulin therapy during follow up.

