10. REGULATORY ISSUES

ETHICS APPROVAL

The study has obtained approval from the Bromley Research Ethics Committee (REC) and Health Regulator Authority (HRA). The study must also receive confirmation of capacity and capability from each participating NHS Trust before accepting participants into the study or any research activity is carried out. The study will be conducted in accordance with the recommendations for physicians involved in research on human subjects adopted by the 18th World Medical Assembly, Helsinki 1964 and later revisions.

CONSENT

Consent to enter the study must be sought from each participant only after a full explanation has been given, an information leaflet offered and time allowed for consideration. Signed participant consent should be obtained. The right of the participant to refuse to participate without giving reasons must be respected. After the participant has entered the study the clinician remains free to give alternative treatment to that specified in the protocol at any stage if he/she feels it is in the participant's best interest, but the reasons for doing so should be recorded. In these cases, the participants remain within the study for the purposes of follow-up and data analysis. All participants are free to withdraw at any time from the protocol treatment without giving reasons and without prejudicing further treatment.

CONFIDENTIALITY

The Chief Investigator will preserve the confidentiality of participants taking part in the study and is registered under the Data Protection Act. After consent is obtained, a letter will be sent to the

participant's GP to inform that she will be taking part in the study. Personal data will only be stored in Trust's files. A specific study code will be used to store anonymised data at Imperial College's Department of Investigative Medicine. Data and all appropriate documentation will be stored for a minimum of 10 years after the completion of the study, including the follow-up period. Blood samples will be handled by NHS Trust regular procedures. Urine samples, collected for research purposes will be stored at Imperial College's Department of Medicine until the study is concluded. After analysis, samples will be disposed in accordance with the Human Tissue Authority's Code of Practice.

INDEMNITY

Imperial College holds negligent harm and non- negligent harm insurance policies which apply to this study.

SPONSOR

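### Early GDM cohort: glycaemic control is judged by need for insulin alone, so a woman managed on another glucose-lowering drug, if any are used, is scored as controlled

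*Combined protocol and SAP*

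**What the plan says.** **Outcome.** The Section 5 outcome list gives "Glycaemic control assessed by need of insulin treatment (yes/no), days to insulin treatment and total insulin dose". For the 28-week visit, Section 6 says that "glycaemic control will be assessed by the need of insulin treatment (yes/no", with days to insulin and insulin dose recorded in women who start it. Under Assessments (iv), Section 6 names the source: "Medical records of women in the Early GDM cohort will be reviewed in order to determine the need of insulin treatment (yes/no) at 28 weeks". The Study Summary agrees.

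**Analysis.** Section 9 states: "For the primary outcome, need for insulin treatment (yes/no), logistic regression analysis will be performed". It adds a days-to-treatment analysis for women who start insulin. It has no rule for any other glucose-lowering drug.

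**Other drugs.** The one restriction is an exclusion criterion in Section 7: "Pre-gestational diabetes or use of anti-diabetic medication in the first visit". Nothing prohibits such drugs after that visit.

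**Care during follow-up.** Section 6: "Women diagnosed with GDM in early pregnancy will continue their routine care under the Obstetric team". Section 5: "They will receive regular antenatal control according to NICE guidelines recommendations". The guideline's treatment sequence is not reproduced. Section 6 also says that treatment information will be taken from the follow-up notes.

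**Other measures in this cohort.** There is no second OGTT. Section 6 specifies HbA1c only with the OGTT bloods. Insulin resistance and urinary C-peptide are mentioned in Section 5 as possible assessments, but they are not measures of glycaemic control.

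**The concern.** The plan labels the outcome glycaemic control but records only one way of losing it. Insulin yes/no equals loss of control on diet and supplement only if insulin is the sole drug used. The protocol neither says nor ensures that, although its own exclusion criterion recognises a wider class of drugs.

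By the written rule, a woman whose glucose was not controlled, and who was then managed on a non-insulin drug, is a success. No planned 28-week glucose measure in this cohort would reveal the difference. The drug is started after randomisation, so randomisation does not guarantee equal use across arms, and in arms this small one or two women move the estimate. At stake is what the trial can conclude: a result on insulin prescribing could be reported as a result on glycaemic control.

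**Working it through.** The plan has no figure to reproduce. Section 9 sets 40 women over both cohorts without a power calculation, and gives no cohort split, event rate or effect size. All rates below are assumptions.

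**1. How the rule codes each woman**

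| Course after randomisation | Insulin (yes/no) | Any glucose-lowering drug (yes/no) |
|---|---|---|
| Diet and supplement alone | No | No |
| Non-insulin drug only | No | Yes |
| Insulin | Yes | Yes |

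The two definitions differ only in the middle row. If that row is empty, there is no problem.

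**2. Small-count illustration.** Assume 10 women per arm (40 split evenly over four groups) and 5 per arm needing drug treatment, so no true effect. One arm has *k* women managed on a non-insulin drug only, the other has none.

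- k = 1: 4/10 v 5/10, odds ratio (4/6)/(5/5) = 0.67
- k = 2: 3/10 v 5/10, odds ratio (3/7)/(5/5) = 0.43

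If the *k* women are in the other arm, the ratios invert: (5/5)/(4/6) = 1.50 and (5/5)/(3/7) = 2.33. A real difference can also vanish: any-drug need of 3/10 v 5/10 becomes 3/10 v 3/10 if two of the five are managed without insulin.

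**3. Range over assumed rates, no true effect.** Let *p* be the share needing any drug (the same in both arms) and *m* the share of those managed on a non-insulin drug only. Then insulin rate = p × (1 − m).

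| p | m = 0.5 v 0.3 | Odds ratio | m = 0.6 v 0.2 | Odds ratio |
|---|---|---|---|---|
| 0.3 | 0.15 v 0.21 | 0.66 | 0.12 v 0.24 | 0.43 |
| 0.5 | 0.25 v 0.35 | 0.62 | 0.20 v 0.40 | 0.375 |
| 0.7 | 0.35 v 0.49 | 0.56 | 0.28 v 0.56 | 0.31 |

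With the any-drug outcome the odds ratio is 1.00 in every row.

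**4. Equal use, real effect.** Assume any-drug rates of 0.30 v 0.60 and m = 0.3 in both arms. The insulin rates are 0.30 × 0.7 = 0.21 and 0.60 × 0.7 = 0.42. The risk ratio stays at 0.50, but the odds ratio moves from (0.30/0.70)/(0.60/0.40) = 0.29 to (0.21/0.79)/(0.42/0.58) = 0.37. Power at 10 per arm (two-sided 0.05) falls from 0.261 to 0.165. With no true effect, equal use leaves the odds ratio at 1.00.

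**5. Against chance.** For 3/10 v 5/10, Fisher's exact p is 0.65. With SE(log OR) = √(1/3 + 1/7 + 1/5 + 1/5) = 0.94, the approximate 95% interval for the odds ratio is 0.07 to 2.7. With a true rate of 50% in two arms of 10, a gap of two or more events arises by chance in about half of trials.

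**The case against.** The strongest objection is that the mechanism needs a fact the documents do not supply. No non-insulin drug is named for follow-up and no frequency is given; if use is close to zero, the point has no practical effect. This stands, and it is why the point is conditional.

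Four stronger readings are tempting, and the documents do not support them.

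- **That prescribers know the allocation and treat the arms differently.** Section 9 leaves researchers unblinded, but treatment is given by the obstetric team, described separately, and Section 5 promises identical sachets. Whether prescribers know the allocation is not stated. Chance remains as a source of unequal use. So does the supplement itself: if it moved women from insulin to another drug, the insulin difference would be partly a real effect.
- **That such drugs also delay insulin or reduce its dose.** No passage says so.
- **That the Consent paragraph in Section 10 licenses them.** It says "the clinician remains free to give alternative treatment to that specified in the protocol at any stage". This is general wording, and the treatment that the protocol specifies is the supplement or placebo. The drugs are simply not prohibited.
- **That insulin must be replaced as the primary outcome.** The Introduction cites reduced need to start insulin with high-fibre diets, so the choice matches the rationale. An any-drug outcome has its own weakness: it treats all drug starts alike and still depends on prescribing thresholds.

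It is also fair to say that the illustrated distortions lie within ordinary chance variation for a pilot of this size, and that the notes review may already capture the data. What remains is that no outcome or analysis uses them, and that following the written rule misclassifies any such woman.

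**Conclusion.** The point holds in conditional form. The early GDM outcome equates glycaemic control with not needing insulin, other glucose-lowering drugs are not prohibited after the first visit, and nothing in the plan separates a woman on such a drug from one on diet and supplement alone. This is more than missing detail, because applying the definition as written gives the wrong code.

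The size is unknown. The odds ratios of 0.67 and 0.43 rest on assumed counts, and the 0.31 to 0.66 range on assumed rates; they show sensitivity, not an expected bias. The direction could be either way, and a false difference requires unequal use. The gap should be closed before analysis. It does not show that the trial's result will be biased. Confidence is moderate, limited by the unknown rate of use.

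**What to change.** 1. In the notes review already planned for this cohort, extract every glucose-lowering drug with its start date.
2. Pre-specify start of any glucose-lowering drug after randomisation (yes/no), with time to start, as an analysis alongside need for insulin. It may be the primary or a key supporting outcome; state which in advance.
3. Report by arm the numbers on diet and supplement alone, on a non-insulin drug only, and on insulin.
4. If insulin alone stays primary, word the outcome and conclusion as need for insulin, not glycaemic control.

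The cost is some outcome wording and one more extraction field. The downside is a broader outcome that treats all drug starts alike, which is why insulin should still be reported beside it. No change to clinical care is implied.

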In the gestational diabetes cohort, where a second OGTT will not be performed, parameters of insulin resistance (HOMA_IR index) and secretion could be assessed using urinary C-peptide obtained from a fasting second-void urine sample at 28 weeks gestation, as described by Oram (20), although these measurements have not been validated in pregnancy.

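### UCPCR is to be calculated with 0-min serum creatinine and no urinary creatinine is ordered, which conflicts with the single-sample urine ratio cited for the insulin secretion outcome

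*Combined protocol and SAP*

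**What the plan says.** All references are to the combined protocol and SAP.

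- **Section 6, Procedures.** Urinary C-peptide is measured in the 0-min and 120-min urine of the OGTT. The text continues "Serum creatinine will be collected at baseline (0 min) and measure in the central lab" and then "The urinary C-peptide creatinine ratio (UCPCR) will be calculated using these data". Creatinine is mentioned once more, two paragraphs earlier, as a baseline-sample test alongside HbA1c and GAD antibodies.
- **Section 6, 2nd visit.** The routine urine work is "Urine sample to test for proteinuria, glycosuria, leucocytes and nitrates". Renal function is listed under blood tests.
- **Section 5, Secondary outcome measures.** For the glucose tolerant cohort, "Insulin secretion will be assessed by second-void fasting UCPCR", following reference 19.
- **Section 6, Assessments (iii).** "Insulin secretion will be estimated by the UCPCR obtained using the fasting second-void urine sample", and "Insulin response will be estimated using the UCPCR calculated with 120 min post-OGTT urine sample". Equation 3 uses both the fasting UCPCR and the mean UCPCR during the OGTT.
- **Section 5, early GDM cohort.** In this cohort, "where a second OGTT will not be performed", secretion could be assessed from "urinary C-peptide obtained from a fasting second-void urine sample at 28 weeks gestation".

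**The concern.** A urinary C-peptide concentration depends on how dilute the urine is. Dividing by creatinine from the same urine removes that dependence, because both concentrations fall together. Dividing by serum creatinine does not. As written, the calculation gives a urine concentration divided by a blood concentration. For the 120-min urine, the denominator also comes from a different time.

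Three measures depend on it: fasting UCPCR (the named insulin secretion outcome in the glucose tolerant cohort), 120-min UCPCR (insulin response) and Equation 3. Assessments (iii) supports UCPCR by its reported correlations with serum insulin and C-peptide, and that support does not carry over to a different ratio. In the early GDM cohort, any 28-week urinary C-peptide would have no creatinine from the same visit, since serum creatinine is tied to the OGTT and this cohort has no second one.

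**Working it through.** The protocol states no SD, effect size or power for these outcomes, so there is no planned figure to reproduce. The check has a textual part and an arithmetic part.

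**1. Where creatinine is ordered**

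| Place in section 6 | Test | Specimen |
|---|---|---|
| 2nd visit, blood tests | renal function | blood |
| 2nd visit, routine urine | protein, glucose, leucocytes, nitrates | urine, no creatinine |
| Procedures, baseline sample | creatinine, listed with HbA1c and GAD antibodies | blood, by context |
| Procedures, urine paragraph | C-peptide at 0 and 120 min | urine, no creatinine |
| Procedures, urine paragraph | creatinine at 0 min | serum |

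The last two rows are the data from which UCPCR is to be calculated. No row gives urinary creatinine.

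**2. Effect of dilution (algebra)**

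Let urine be diluted by a factor d, so that both urinary concentrations are divided by d.

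- Same-sample ratio: (C/d) / (K/d) = C/K, which does not depend on d.
- Serum denominator S: (C/d) / S. At d = 2 the index is halved, and at d = 3 it falls to one third.
- Equation 3 is proportional to 1/√(U0 × mean U). If both urines are diluted twofold, it is multiplied by 1/√(0.5 × 0.5) = 2. If only the fasting urine is diluted, and the two ratios were equal, it is multiplied by 1/√(0.5 × 0.75) = 1.63.

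**3. Size for the fasting index (assumed inputs)**

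Let s be the log-SD of urine dilution and t the log-SD of the true ratio. Neither is in the protocol; s = 0.4 to 0.7 and t = 0.4 to 0.6 are assumed, first as independent.

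- Dilution share of variance = s²/(s² + t²)
- Variance factor = (s² + t²)/t²
- Correlation with the true ratio = t/√(s² + t²)
- Information kept = t²/(s² + t²)

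| s | t | Share | Factor | Correlation | Information kept |
|---|---|---|---|---|---|
| 0.4 | 0.6 | 0.16/0.52 = 30.8% | 0.52/0.36 = 1.44 | 0.83 | 69.2% |
| 0.5 | 0.5 | 0.25/0.50 = 50.0% | 0.50/0.25 = 2.00 | 0.71 | 50.0% |
| 0.7 | 0.4 | 0.49/0.65 = 75.4% | 0.65/0.16 = 4.06 | 0.50 | 24.6% |

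The first and last rows are the extremes of the assumed range. Dilution is more than half the variance only when s > t. With less dilution the loss is small: s = 0.2 and t = 0.5 gives 0.29/0.25 = 1.16.

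If dilution and the true ratio correlate at r, the factor is (s² + t² + 2rst)/t²:

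- s = 0.4, t = 0.6: 1.04 at r = −0.3 and 1.84 at r = +0.3.
- s = 0.7, t = 0.4: 3.01 at r = −0.3 and 5.11 at r = +0.3.

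**4. Size for Equation 3**

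On the log scale its UCPCR part is −0.5 × [ln U0 + ln mean(U0, U120)]. This was simulated with 400,000 women per setting. The assumptions were a 120-min to fasting fold of 2 or 4, a 0-to-120-min correlation of 0.5 or 0.8 for the true ratios, and of 0 or 0.5 for dilution. The variance factor was:

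- 1.26 to 1.45 at s = 0.4, t = 0.6;
- 1.58 to 2.01 at s = t = 0.5;
- 2.80 to 4.10 at s = 0.7, t = 0.4.

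These factors are for the UCPCR part alone. The glucose terms are left out, so they are not the factors for the whole index.

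**The case against.** The strongest reply is that serum is a slip for urinary. The abbreviation is expanded as a urinary ratio, Assessments (iii) ties it to named urine samples, and a blood creatinine is already listed earlier in Procedures, so a second serum order inside the urine paragraph looks redundant. That reading of the intent is plausible. It does not repair the instruction: a laboratory following Procedures would assay no urinary creatinine, and the ratio would be formed from what it did assay.

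Other points limit the concern:

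- Every input to the size calculation is assumed. The model ignores variation in serum creatinine and treats urinary creatinine as removing dilution completely. The result runs from almost no loss to about fivefold variance, so it is an illustration and not an estimate for this trial.
- The measures are secondary, in a 40-woman pilot without a power calculation. Serum insulin and C-peptide at 0 and 120 min remain available.
- Section 10 keeps the urine until the study is concluded, so there is time to correct this, though not indefinitely.
- In the early GDM cohort the measure is optional, and the 28-week visit text lists no urine collection. That part matters only if the sample is taken.
- The conflict with the cited method rests on the printed title of reference 19 and the protocol's own definitions; the paper itself was not available.

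**Conclusion.** The concern holds. The calculation rule in Procedures conflicts with the per-sample urine ratio in section 5 and Assessments (iii), and no urinary creatinine is ordered anywhere. That dilution no longer cancels is algebra and needs no assumption. The size does: for s = 0.4 to 0.7 and t = 0.4 to 0.6, independent, the fasting index has 1.4 to 4.1 times the variance of the true ratio, and 1.0 to 5.1 times if the two correlate between −0.3 and +0.3. The UCPCR part of Equation 3 has 1.3 to 4.1 times the variance.

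The consequence is mainly lost precision. The arm comparison would be biased only if urine concentration differed by arm, which nothing in the protocol suggests. GDM at 28 weeks, need for insulin, and Equations 1 and 2 are unaffected. The point should be fixed because it undermines a named secondary outcome and is cheap to correct.

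**What to change.** Replace the creatinine and UCPCR sentences in section 6, Procedures, with: *Urinary creatinine will be measured in the same urine sample as each urinary C-peptide. UCPCR = urinary C-peptide / urinary creatinine from that sample, in pmol/mmol.*

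Apply it as follows:

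1. All women: 0-min and 120-min urine at the first OGTT.
2. Glucose tolerant cohort: 0-min and 120-min urine at the 28-week OGTT.
3. Early GDM cohort: the single fasting second-void sample at 28 weeks, if it is collected.

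Remove serum creatinine from the UCPCR calculation and keep it only as a renal function test.

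The cost is a wording change and one inexpensive assay on urine already due to be collected and stored at −80 °C. It needs no extra visit. In the early GDM cohort it adds a 28-week assay only if the optional sample is taken. The assay must be run before the urine is disposed of under section 10 (Confidentiality).
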